The Neural Effects of Balance Versus Aerobic Training in Individuals With Degenerative Cerebellar Diseases

NCT05002218

February 21, 2025

BACKGROUND

Abstract

Exercise is the main treatment for degenerative cerebellar diseases, a group of disorders that affect cerebellar neurons causing an array of symptoms including an inability to coordinate balance, gait, and extremity movements. Studies researching the effect of balance training on degenerative cerebellar disease have found functional improvements in patient's walking.

The role of aerobic exercise in the treatment of degenerative cerebellar disease is relatively unknown. Research on rats with symptoms similar to cerebellar ataxia indicates that moderate aerobic exercise increases the rat's lifespan compared to rats that do not exercise. Studies of other neurological diseases, such as Parkinson's disease, illustrate that aerobic exercise enhances motor learning in the brain. Only one study to date has assessed the effectiveness of aerobic exercise on cerebellar ataxia in humans. Patients were given a 4-week cycling regime consisting of 15 minutes per day, 3 days per week. Results indicated that patients in the cycling group had improved ICARS scores (a scale used to monitor ataxia), but not gait speed or standing capacity compared to a control group. Other measures of balance were not tested in this study. The main objective of this project will be to compare the benefits of aerobic versus balance training in DCD. We hypothesize that both aerobic and balance training will improve function in ataxic subjects, but that the mechanisms in which these improvements occur differ.

Study Purpose and Rationale

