Heredity spinocerebellar diseases are a group of disorders in which cerebellar degradation manifests in ataxia, a neurological sign causing impaired coordination and balance.¹ The diseases are devastatingly debilitating with many individuals requiring wheelchairs for locomotion after only 10 to 15 years from initial diagnoses. With no disease modifying medications currently available, balance training is recommended to improve motor skills and maintain function. Yet, recent emerging evidence from our research group shows that aerobic training is a promising treatment option. The goal of this study is to compare the impact of balance versus aerobic training on the brains of individuals with hereditary spinocerebellar diseases. Prior research has used clinical measures, such as the Scale for the Assessment and Rating of Ataxia (SARA), to determine the benefits of training. Although validated for this purpose, these scales

cannot differentiate between functional compensation of deficits versus slowing of cerebellar degradation. Thus, it is important to examine the neurological impact of different training methods to distinguish whether one training method is better able to slow disease progression than the other. Moreover, we speculate that aerobic and balance training impact the brain via different mechanisms. Two hypotheses exist regarding the neural effects of training; the degenerating cerebellum undergoes neuroplastic changes to adapt its functioning, or alternatively, other brain areas undergo neuroplastic changes to compensate for deficits. We hypothesize that balance training causes improvements for people with cerebellar degeneration by impacting brain structures outside the cerebellum whereas aerobic training induces neuroplastic changes within the cerebellum. We expect this result because:

1) A 2-week balance training program resulted in increased grey matter volume in the premotor cortex of individuals with cerebellar degeneration, but no statistically significant changes in the cerebellum.

2) Ataxic animals that regularly perform aerobic exercise have larger cerebellums with increased synapses and dendrites at death than those who are sedentary.

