3) Preliminary data from our group indicates increased cerebellar volume in individuals with spinocerebellar disease who participate in a 6-month home aerobic program, but decreased volume for those who perform balance training. Thus, if our hypothesis is true, aerobic training may have more influence on disease progression than balance training as it directly impacts the cause of deficits, the cerebellum.

Public Health Significance: There is a critical need to determine effective treatments for hereditary cerebellar diseases. Research has shown balance and aerobic training improves symptoms for individuals with these disorders, but the mechanisms of improvement are unknown. This proposal will begin to examine the impact of both training methods on the brain. By understanding how each training method impacts cerebellar volume, microstructure, and functional connectivity, future research can more precisely target training regimens with the goal of slowing the disease progression of individuals with these devastating diseases.

Research Aims & Abstracts

AIM 1) To determine the effect of training on cerebellar volume. Individuals with hereditary spinocerebellar ataxias will be randomized to either a 6-month home aerobic or balance

training program. Structural MRI scans will be taken before and after the training programs to determine the impact of training on cerebellar volume. We hypothesize that aerobic training will slow cerebellar volume loss when compared to balance training.

AIM 2) To evaluate the long-term training effects on clinical measures of ataxia and correlate changes with cerebellar volume. SARA scores will be determined before and after each training program. They will also be taken at 3- and 6-months post-training along with structural MRI scans. Consistent with our prior research, we hypothesize that improvements in SARA scores will revert back to baseline if training is halted. We further hypothesize that changes in SARA scores will correlate with cerebellar volume changes in the aerobic group, but not with changes in the balance group.

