All analysis will be conducted blind to which intervention is being evaluated. SAS (version 9.4) will be used for all statistical analyses. We will use intention to treat principles. Demographic and clinical variables will be compared using the Wilcoxon's test and chi-squared analysis for continuous and categorical variables, respectively. The association between cerebellar volume change and SARA score change will be estimated with Spearman's correlation coefficient. We will use linear mixed-effect regression analysis to test whether change in cerebellar volume differed between training groups, controlling for age and other co-variates mentioned above as fixed effect. To account for within-subject correlation due to repeated measurement, we will include a random

intercept. If the assessment effect is significant ($p < 0.05$), post hoc analysis will be performed using pairwise comparisons between assessments.

For diffusion tensor imaging, individual ANCOVAs will be determined for FA and MD in the middle of both hemispheres for the regions of interest, with age, gender, and disease type as covariates.

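### Aim 2 predicts a volume–SARA correlation in the aerobic arm but not in the balance arm, and no between-arm comparison of the correlations is planned

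*Combined protocol and SAP*

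**What the plan says.** Under Research Aims & Abstracts, Aim 2 states the hypothesis that "changes in SARA scores will correlate with cerebellar volume changes in the aerobic group, but not with changes in the balance group". It follows from the study's central idea. The Abstract expects both trainings to help, "but that the mechanisms in which these improvements occur differ", and Study Purpose and Rationale places the balance effect outside the cerebellum, "whereas aerobic training induces neuroplastic changes within the cerebellum".

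Statistical Procedures gives the association one sentence: "The association between cerebellar volume change and SARA score change will be estimated with" Spearman's correlation coefficient. It does not say whether the coefficient is computed by arm, over which interval change is measured, or whether a confidence interval is given. SARA and structural MRI are done before and after training, and Aim 2 adds: "They will also be taken at 3- and 6-months post-training along with structural MRI scans". With four time points, change can be defined in several ways.

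The same section describes a linear mixed model "to test whether change in cerebellar volume differed between training groups". That model serves Aim 1. It names no SARA term, so it does not compare the volume–SARA relation between arms.

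**The concern.** The Aim 2 hypothesis is a contrast: the relation is present in one arm and absent in the other. Evidence for it has to come from comparing the arms. Two coefficients set side by side do not supply that. A clear result in one arm and an unclear one in the other can easily arise when the true correlations are equal, because each arm is small. A coefficient near zero, or a p-value above 0.05, in about 19 people also does not show that there is no correlation.

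At stake is the mechanistic conclusion, that aerobic training works through the cerebellum and balance training does not. Without a stated comparison, that conclusion could rest on the contrast between two noisy estimates. The change interval and the form of the comparison could also be chosen after the results are known.

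**Working it through.** **The plan's own figure.** The documents give no sample size or power for the correlation. The Sample Size Calculation concerns volume change only: difference 1.34, SD 1.3, α = 0.05 (two-sided assumed), power 0.80. The two-sample t calculation gives 15.8, so the stated 16 per group reproduces. Dropout of 20% gives 16/0.8 = 20, also as stated.

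**Inputs.** Recruited: 24 per arm. Less 20% dropout: 24 × 0.8 = 19.2, so 19 per arm. 16 per arm is used as the lower case. The documents give no correlation, so a range is assumed. Only absolute size is shown, because the sign does not affect the results.

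**If one coefficient were computed on everyone.** With equal arm means, the pooled value is roughly the average of the two arm values:
- aerobic 0.6, balance 0: (0.6 + 0)/2 = 0.30
- 0.3 in both: (0.3 + 0.3)/2 = 0.30
- aerobic 0, balance 0.6: (0 + 0.6)/2 = 0.30

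Simulation (40,000 trials per case, 19 per arm) gives a mean Spearman of about 0.29 in all three cases, significant in about 44%. If mean volume change differs between arms by 1.34/1.3 = 1.03 SD, all three fall to about 0.26. The predicted pattern, equal correlations and the reverse pattern therefore look the same.

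**If one coefficient is computed per arm.** On the Fisher z scale, the standard error for Spearman is SE = √(1.06/(n − 3)). With n = 19, SE = √(1.06/16) = 0.257. The probability that one arm is significant at two-sided 0.05 is

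p = Φ(atanh(ρ)/SE − 1.96) + Φ(−atanh(ρ)/SE − 1.96).

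With the same true ρ in both arms, the chance of a significant aerobic arm and a non-significant balance arm is p(1 − p). Example at ρ = 0.3: atanh(0.3) = 0.310; 0.310/0.257 = 1.20; p = 0.225; p(1 − p) = 0.225 × 0.775 = 0.17.

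| Equal true ρ | p (one arm significant) | p(1 − p) | Simulated |
|---|---|---|---|
| 0 | 0.050 | 4.8% | 5% |
| 0.2 | 0.124 | 10.8% | 11% |
| 0.3 | 0.225 | 17.5% | 18% |
| 0.45 | 0.469 | 24.9% | 25% |
| 0.6 | 0.768 | 17.8% | 17% |
| 0.7 | 0.921 | 7.3% | 7% |
| 0.8 | 0.990 | 1.0% | 1% |

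A direct between-arm Fisher z test rejects in 4.4%, 4.9% and 5.3% of the simulated trials at equal ρ of 0.3, 0.45 and 0.6, close to the nominal 5%.

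**What a non-significant balance arm shows.** At ρ = 0.3 the chance of non-significance is 1 − 0.225 = 77%. An observed coefficient of 0 with n = 19 has a 95% CI of ±tanh(1.96 × 0.257) = ±0.47. An observed 0.6 has a 95% CI of about 0.19 to 0.83.

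**Power of the direct comparison, 0.6 versus 0.** The SE of the difference is √(2 × 1.06/(n − 3)).
- n = 19: SE = 0.364; 0.693/0.364 = 1.90; power about 48%. Simulation gives 47.6% for the difference in correlations and 49.5% for a regression interaction.
- n = 16: SE = 0.404; 0.693/0.404 = 1.72; power about 40%. Simulation gives 39.4% and 41.5%.

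**The case against.** The strongest reply is that Aim 2 and the statistical section should be read together. Aim 2 frames the association by arm, and the statistical section names the statistic for it, so the plan is one coefficient per arm. That is fair. A reader might infer that the plan pools the arms and so cannot address its hypothesis. The documents do not say so, and the pooled figures only show why the words by arm should be added.

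Second, the plan says the association will be estimated. It sets no p-value threshold for the correlation and no rule of significance in one arm only. This also stands. A reader might infer that the investigators have committed to that rule, but the text does not support it. The percentages in the table show what would happen if it were used. They are also high only for mid-range correlations: with equal correlations near 0, or at 0.7 and above, the misleading pattern is uncommon.

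Third, the direct comparison has low power, so it may settle little. This is true, but it is a reason to word the conclusion cautiously. It does not make two separate coefficients adequate evidence of a difference.

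What survives all three replies is that the hypothesis concerns a difference between arms and the documents contain no comparison that addresses it.

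**Conclusion.** The point holds in limited form. The stated analysis can describe the volume–SARA association, but it does not include the between-arm comparison that the Aim 2 hypothesis needs. If separate p-values were used, significance in the aerobic arm only would occur with equal true correlations in about 1% to 25% of trials at 19 per arm, with the peak near 0.45. These figures rest on assumed correlations, bivariate normal changes, 19 analysed per arm and a decision rule that the plan does not state.

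A reader might also extend this to Aim 1, or to the sentence that opens post hoc pairwise comparisons when the assessment effect is significant. The documents do not support that. Aim 1, that "aerobic training will slow cerebellar volume loss when compared to balance training", has its own between-group test in the mixed model, which does not depend on the post hoc step. The post hoc sentence concerns comparisons between assessments and does not bear on the correlation. The matter is worth correcting before analysis, and it affects only the strength of the Aim 2 mechanistic claim.

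**What to change.** Add three or four sentences to Statistical Procedures:

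1. Spearman's coefficient will be reported separately for each arm with a 95% CI, for one named change interval (for example baseline to end of training).
2. Any statement that the arms differ will rest on a direct comparison, either the difference in correlations or a volume-change-by-group interaction in a model for SARA change, reported with its CI. Choose one in advance.
3. A non-significant coefficient in the balance arm will not be interpreted as absence of correlation. The CI will be used to say which values remain plausible.

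This needs no extra data and changes no study procedure. The cost is a more cautious Aim 2 conclusion. Even for a contrast as large as 0.6 versus 0, the comparison has about 40% power with 16 per arm and 47–50% with 19, and the by-arm intervals will be wide.

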Exploratory Aim 3) To examine the effects of exercise on cerebellar microstructure and functional connectivity to the cerebellum. Diffusion weighted imaging and resting state fMRI scans will be taken before and after individuals with spinocerebellar disease participate in a 6-month home aerobic or balance training program. We will then use the cerebellum as our region of interest to analyze how training impacts cerebellar microstructure and functional cerebellar connections. Although the impact of training on the cerebellum has been investigated in healthy individuals, it is unclear how training will impact the degenerating cerebellum in our subject population. Thus, we will use this preliminary data to determine which cerebellar regions and functional networks are most impacted by training to form targeted hypotheses for future research projects.

STUDY DESIGN

This is a single-blinded randomized control trial. After initial testing, participants will be randomly assigned to either home balance or aerobic training for 6 months. After training, individuals will undergo post-training testing. At the post-training testing, individuals will be encouraged to continue training, but not required to as part of the study. Follow-up testing will then be conducted at 3- and 6-month post-training to evaluate the longevity of training effects.

The rationale for this study design is as follows:

1) Randomization between balance and aerobic training groups will balance known and unknown confounding factors that may influence changes in cerebellar volume. Individuals

conducting assessments will be blinded to group, but participants cannot be blinded given the nature of the intervention.

2) Although the use of an active control (balance training) as opposed to a placebo control may make it more difficult to detect differences between groups, our preliminary data made us comfortable that we would be able to detect differences. This design also allows us to examine the neural mechanisms underlying balance training effects on individuals with spinocerebellar disease in addition to aerobic training.

3) 6-months of training was used for this study because prior work in our laboratory on healthy individuals showed that 6-months of training was long enough to detect statistically significant changes in brain volume.

4) Follow-up testing was selected to start at 3 months post-training because our prior research showed that clinical effects were still seen at this timepoint.

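### The Aim 2 correlation of volume change with SARA change is not adjusted for disease type, so types that decline faster on both measures could produce it within an arm

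*Combined protocol and SAP*

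**What the plan says.** Research Aims & Abstracts, AIM 2, predicts that "changes in SARA scores will correlate with cerebellar volume changes in the aerobic group, but not with changes in the balance group". The analysis for this is one sentence under STATISTICAL PROCEDURES: "The association between cerebellar volume change and SARA score change will be estimated with" Spearman's coefficient. It names no covariate, stratum or partial version. It does not say whether the coefficient is computed by arm or pooled, and the section contains no test of the difference between two coefficients.

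Other analyses in the section are adjusted. The mixed model for cerebellar volume is fitted "controlling for age and other co-variates mentioned above as fixed effect", though no list of those covariates precedes the sentence. The diffusion imaging ANCOVAs are run "with age, gender, and disease type as covariates". Both phrases belong to their own models and cannot be read across to the correlation. Baseline SARA is not named as a covariate for any analysis.

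STUDY DESIGN gives the role of randomisation: "Randomization between balance and aerobic training groups will balance known and unknown confounding factors that may influence changes in cerebellar volume". That statement concerns comparisons between arms.

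**The concern.** The volume-SARA association compares participants within an arm. Both variables are changes observed after baseline, and neither is assigned at random, so randomisation does not remove their common causes. Study Purpose and Rationale describes the population as several disorders. If some types lose cerebellar volume faster and also worsen faster on SARA, pooling the types produces a correlation even where none exists within any type. Its direction is the one that Aim 2 expects, with more volume loss accompanying more worsening. Age and baseline severity could act in the same way.

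The correlation is the link between the imaging result and the clinical result. It would be read as support for the idea that aerobic training helps through the cerebellum. The plan already treats disease type as relevant to cerebellar outcomes in the diffusion analysis, yet omits it from an analysis that is more exposed to it.

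**Working it through.** **The plan's sample size.** Sample Size Calculation gives a difference of 1.34, SD 1.3, alpha 0.05 and beta 0.2. Two-sided, n = 2 × (1.96 + 0.84)² × 1.3² / 1.34² = 14.8, so 15 by the normal approximation. The t-test version gives 15.8, so the stated 16 per group is reproduced. It was sized for the volume difference; no calculation is given for the correlation. The plan's own figures of 16, 20 and 24 per arm are used below.

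**Assumptions, because the documents give no decline rates or mix by type.** Two types, each with probability 0.5, differ by d within-type SDs on both changes. Both changes are scored so that larger means more decline. There is no association within type.

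**Induced correlation.** With a fraction p of the faster type, the Pearson value is p(1−p)d² / [1 + p(1−p)d²]. At p = 0.5:

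- d = 0.5: 0.0625/1.0625 = 0.06
- d = 1: 0.25/1.25 = 0.20
- d = 1.5: 0.5625/1.5625 = 0.36
- d = 2: 1/2 = 0.50

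**Simulation.** For each setting, 20,000 trials of two arms were generated. The unadjusted p-value uses t with n−2 df. The adjusted one correlates the residuals of the ranks on type, with n−3 df. The direct test is (atanh r₁ − atanh r₂)/√(2 × 1.06/(n−3)) on the unadjusted coefficients, compared with 1.96.

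| n per arm | d | Mean Spearman | Significant, unadjusted | Significant, adjusted for type | Aerobic significant, balance not (unadjusted) | Direct test of difference (unadjusted) |
|---|---|---|---|---|---|---|
| 16 | 0 | 0.00 | 4.9% | 5.1% | 4.7% | 4.6% |
| 16 | 0.5 | 0.05 | 5.5% | 5.2% | 5.2% | 4.5% |
| 16 | 1 | 0.19 | 11.0% | 5.0% | 9.8% | 4.3% |
| 16 | 1.5 | 0.36 | 28.6% | 5.2% | 20.5% | 4.0% |
| 16 | 2 | 0.50 | 55.2% | 5.5% | 24.7% | 3.1% |
| 20 | 1 | 0.19 | 13.2% | 5.2% | 11.4% | 4.0% |
| 20 | 1.5 | 0.36 | 35.9% | 5.1% | 23.4% | 4.1% |
| 24 | 1 | 0.20 | 15.5% | 4.9% | 13.0% | 4.5% |
| 24 | 1.5 | 0.37 | 44.0% | 5.2% | 24.9% | 4.0% |

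The sixth column is close to q(1−q), where q is the unadjusted rate: 0.110 × 0.890 = 0.098 and 0.286 × 0.714 = 0.204. Two independent p-values fall on opposite sides of 0.05 that often, although the expected correlation is the same in both arms. The direct test does not exceed 5%.

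**How large these type differences are.** If 1.3 is the total SD of percent volume change, the within-type SD is 1.3/√(1 + 0.25d²). Then d = 1 is 1.3/√1.25 = 1.16 percentage points over six months, and d = 1.5 is 1.5 × 1.3/√1.5625 = 1.56. With the balance group's pilot SD of 0.53 they are 0.47 and 0.64. The balance group's mean pilot loss was 1.06%. With 1 SD on volume but only 0.5 SD on SARA, the induced correlation is about 0.11 and the rejection rate about 7%.

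**Cost of adjusting.** The critical coefficient is t/√(df + t²), with df = n−2−k for k covariates.

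| n | k = 0 | k = 2 | k = 4 |
|---|---|---|---|
| 16 | 0.50 | 0.53 | 0.58 |
| 20 | 0.44 | 0.47 | 0.50 |

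At n = 16 and a coefficient of 0.5, the 95% interval (Fisher z, variance 1.06/(n−3−k)) is −0.01 to 0.80 unadjusted, −0.03 to 0.81 with one covariate and −0.09 to 0.83 with three.

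**The case against.** The strongest reply is that Aim 2 predicts a contrast between randomised arms. Confounding by type is expected equally in both, so it cannot on average produce a correlation in one arm only. This is correct, and the direct test bears it out. It does not rescue the plan as written, because the plan contains no such test. Separate coefficients would be reported, and each carries the induced correlation.

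The size is also open to challenge. Nothing in the documents shows that types differ by 1 SD on both measures. At 0.5 SD the effect is negligible, and at the larger SD, differences of 1 or 1.5 SD exceed the whole mean loss in the balance group. This stands: the risk is conditional. The plan also speaks of estimating the association and claims no power for it. That lowers the stakes, but an estimate shifted by type is still shifted.

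Two stronger readings are tempting, and the documents support neither:

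- A reader might infer that this is the only Aim 2 claim that randomisation leaves unprotected. The other Aim 2 hypothesis is also a before-after claim: "we hypothesize that improvements in SARA scores will revert back to baseline if training is halted". It is assessed after training has become optional, when "individuals will be encouraged to continue training, but not required to as part of the study".
- A reader might infer that a chance excess of a fast-declining type in one arm would yield the predicted pattern. The induced correlation depends on p(1−p), so it is largest at an even split and an excess lowers it. In simulation with d = 1.5 and n = 16, the mean Spearman value is 0.38 at an even split and about 0.28 with either 75% or 25% of the fast type. Arms imbalanced in opposite directions would show the same correlation.

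**Conclusion.** The point holds as a minor one. The volume-SARA coefficient is unadjusted for disease type, age and severity, and randomisation does not protect it within an arm. Under the stated assumptions at 16 per arm, the false-positive rate is about 5.5%, 11% or 29% for shared type differences of 0.5, 1 or 1.5 SD, and about 5% once type is adjusted for. At a given type difference of 1 SD or more, the rate rises with more participants.

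The documents do not support saying that confounding by type would by itself explain a difference between arms. What they leave open is that the difference would be judged from two p-values, which gives the predicted pattern in about 10% or 21% of trials at 1 or 1.5 SD, against 4.7% without confounding.

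These sizes rest on two equally common types, equal shifts on both measures and a type variable that captures the whole difference. Only type was simulated; age and severity follow the same reasoning without a figure.

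**What to change.** State in STATISTICAL PROCEDURES that the Aim 2 correlation is computed within each arm as a partial Spearman coefficient (SAS PROC CORR, SPEARMAN with PARTIAL), given age and disease type in two classes fixed beforehand. Add baseline SARA only if numbers allow. Report the confidence interval and show the unadjusted coefficient beside it. Keep the arms separate, because pooling would add training arm as a further confounder.

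Judge the aerobic-but-not-balance prediction by a direct test of the difference between the two coefficients, or by an arm-by-volume-change interaction. Adjustment alone would still leave two p-values to compare.

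The cost is a few sentences in the SAP, using data the trial already collects, and a small loss of precision: with two covariates the critical value goes from 0.50 to 0.53 at 16 per arm and from 0.44 to 0.47 at 20. The direct test has limited power. With 16 per arm and two covariates its standard error is √(2 × 1.06/11) = 0.44, so against a balance coefficient of zero the aerobic coefficient must reach about tanh(1.96 × 0.44) = 0.70. The comparison is therefore best labelled exploratory.

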Diffusion Tensor Imaging: This measure will be a primary outcome of Aim 3. Diffusion data will be preprocessed for motion and corrected for geometrical distortion using ExploreDTI. For each participant, the bmatrix will be reoriented to provide a more accurate estimate of diffusion tensor orientations. Diffusion tensor estimation will be performed using a non-linear least square fitting method. FA and Mean Diffusivity (MD) maps will be generated. Whole brain tractography will be performed using all brain voxels with FA 0.2 as seed region. Streamlines will be propagated using an Euler integration tractography algorithm with a step size of 0.5 mm and with an angular

and anisotropy threshold of 45 degrees and FA 0.2 respectively. Finally, diffusion tensor maps and whole brain tractography will be exported to TrackVis version 0.5.2.2 for manual dissection and quantification of cerebellar fiber tracts.

To determine cerebellar fiber tracts, we will use TrackVis to select regions of interest in the b0 images. The anatomical structure corresponding to the desired regions of interest will be initially localized in MRI atlases of the cerebellum, subsequently identified in T1 images, and then selected in the co-registered b0 dataset. The following regions of interest will be selected: 1) fastigial nucleus, 2) interpositus nucleus, 3) superior cerebellar peduncle, 4) middle cerebellar peduncle, and 5) inferior cerebellar peduncle. In order to extract clean diffusion measurements avoiding crossing and complex white matter regions, regions of interest will be selected using a manual two region approach.

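### The DTI ANCOVAs leave out the pre-training FA or MD of the same region, which loses precision, and the plan does not say what the response is

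*Combined protocol and SAP*

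**What the plan says.** The DTI analysis is one sentence in Statistical Procedures: "individual ANCOVAs will be determined for FA and MD in the middle of both hemispheres for the regions of interest". The same sentence ends with the adjustment: "with age, gender, and disease type as covariates". It does not name the response variable, a significance level or the number of tests.

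Three other places bear on it:

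- Research Aims & Abstracts, Exploratory Aim 3, fixes the timing: "Diffusion weighted imaging and resting state fMRI scans will be taken before and after individuals with spinocerebellar disease participate" in the 6-month programmes. A pre-training value is therefore planned for each participant.
- Study procedures, Diffusion Tensor Imaging, names five regions: "1) fastigial nucleus, 2) interpositus nucleus, 3) superior cerebellar peduncle, 4) middle cerebellar peduncle, and 5) inferior cerebellar peduncle". It also states that "FA and Mean Diffusivity (MD) maps will be generated", and it ranks DTI within its aim: "This measure will be a primary outcome of Aim 3".
- Exploratory Aim 3 gives the use of the results: "we will use this preliminary data to determine which cerebellar regions and functional networks are most impacted by training to form targeted hypotheses" for later projects.

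**The concern.** The pre-training FA or MD of a tract is likely to be the best single predictor of its post-training value. The plan collects it, yet does not list it among the covariates. Participants with different disease types and severity can be expected to differ in tract integrity before training starts. If the response is the post-training value, most of that spread stays in the error term. Any chance imbalance between the randomised groups then passes into the estimated training effect.

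The stake is how well the DTI data can rank regions. Imprecise estimates make it harder to tell which tracts responded, and that ranking is the stated purpose of Aim 3. Because the response is undefined, two analysts could also follow the plan and fit different models with quite different precision.

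**Working it through.** **The plan's own figures.** There is no sample size, power or error rate for DTI to reproduce. The nearest figure is the 16 per group for cerebellar volume. A difference of 1.34, SD 1.3, alpha 0.05 (two-sided assumed) and 80% power give 15.8 per group by the two-sample t-test, so 16 is reproduced. Recruitment of 24 per group with 20% dropout leaves 24 × 0.8 = 19.2, so I use 20 per group below.

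**Inputs.** Let σ² be the variance of FA (or MD) in a region, taken as equal before and after training, and let r be the pre-post correlation. The documents give no r, so 0.5 to 0.9 is an assumed range.

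**Error variance under three models**

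- Post-training value, no baseline: σ²
- Change, no baseline: 2σ²(1 − r)
- Post-training value with baseline as covariate: σ²(1 − r²)

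Adding baseline therefore removes r² of the variance in the first model. In the second it removes 1 − (1 − r²)/[2(1 − r)] = (1 − r)/2.

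| Assumed r | Removed if response is post value | SE multiplier, √(1 − r²) | Removed if response is change |
|---|---|---|---|
| 0.5 | 25% | 0.87 | 25% |
| 0.7 | 49% | 0.71 | 15% |
| 0.8 | 64% | 0.60 | 10% |
| 0.9 | 81% | 0.44 | 5% |

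These figures make no allowance for age, gender and disease type. Strictly, r should be the partial correlation given those three, so the gain is smaller if they already explain part of the variance.

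**What this means for power.** Take a true difference of 0.5 SD of the post-training value, 20 per group and a two-sided 0.05 (assumed for DTI):

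| Assumed r | Post value only | Change | Post value with baseline |
|---|---|---|---|
| 0.7 | 34% | 51% | 58% |
| 0.8 | 34% | 68% | 73% |
| 0.9 | 34% | 93% | 94% |

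**Chance baseline imbalance.** With 20 per group, the standard error of the baseline difference is √(2/20) = 0.32 SD. Suppose the groups differ by that much at baseline. A post-only comparison is shifted by r × 0.32, that is 0.22 SD at r = 0.7 and 0.28 SD at r = 0.9. A change comparison is shifted the other way by (1 − r) × 0.32, that is 0.09 or 0.03 SD. The baseline-adjusted model removes the shift. Over repeated randomisations these shifts average to zero and are already in the standard error, so the type I error rate is unaffected.

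**Number of tests (secondary).** Five regions × two hemispheres × two metrics = 20. If hemispheres are combined, 5 × 2 = 10. The plan states neither count. At 0.05 with no region affected, the expected number of false positives is 20 × 0.05 = 1, or 10 × 0.05 = 0.5, whatever the correlation between tests.

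**The case against.** **The response may be change.** The plan does not exclude it. A group-by-time test on the two scans would amount to the same comparison. Baseline is then already largely used, and the gain is 15% or less once r reaches 0.7. This stands, and it is why the 49% to 81% cannot be quoted alone.

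**ANCOVA may imply baseline adjustment.** In a pre-post trial many readers would take it so. But the covariate list is explicit and baseline is not on it. If adjustment is intended, a few words would settle the matter.

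**The tempting stronger reading.** A reader might infer that the regions picked will often be chance findings, because some 20 tests are run without error control and without baseline. The documents do not support that:

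- Omitting a baseline covariate does not inflate false positives under randomisation. Low power raises the share of chance findings only indirectly.
- The chance of at least one false positive is 1 − 0.95^20 = 64% only if the tests are independent, no region is affected and each is tested at 0.05. With a common correlation of 0.3, 0.5, 0.7 or 0.9 it is about 54%, 42%, 29% or 15%. With 10 independent tests it is 40%.
- No DTI threshold is stated. The 0.05 levels in the analysis text belong to the mixed model's assessment effect and to the fMRI clusters. Choosing the regions most affected could mean ranking by estimate.
- The share of flagged results that are chance is a different quantity. Assume 20 tests at 0.05, 20 per group, true effects of 0.5 to 0.8 SD and 2 to 10 real effects. That share then runs from about 57% down to 7%.

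The family-wise correction for resting fMRI is a weak comparator, because it addresses a search over every voxel and not five named regions. Aim 3 is also labelled exploratory, and its output only forms hypotheses. Strict control would be costly: with 20 per group, Bonferroni over 20 tests (0.0025 each) raises the difference detectable at 80% power from 0.91 to 1.30 SD. Formal multiplicity control is therefore a choice for the sponsor and not a defect to be corrected.

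**Conclusion.** The point holds for the baseline covariate and the unstated response. The listed covariates omit the pre-training FA or MD, which is collected. Including it improves precision in large samples under either reading of the response. The gain is large for a post-training response (49% to 81% of error variance at r = 0.7 to 0.9) and modest for change (15% down to 5%).

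These sizes rest on the assumed correlations, on equal variances before and after training, and on no allowance for the three covariates already in the model. The omission loses precision and leaves chance imbalance unadjusted. It does not bias the randomised comparison or raise its error rate. The effect is confined to exploratory Aim 3, so this is a worthwhile improvement and not a threat to the trial's main conclusions.

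**What to change.** State in Statistical Procedures that the response in each DTI ANCOVA is the post-training FA (or MD) of the region. Add the pre-training value of the same region and metric as a covariate beside age, gender and disease type. This needs no new scans, visits or participants. The cost is one degree of freedom per model.

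Optional, given the exploratory status of Aim 3: state the number of tests (20, or 10 if hemispheres are combined) and note that about one (or 0.5) false positive is expected at 0.05 if no region is affected. Report estimates with confidence intervals. Then either give false-discovery-rate q-values beside the raw p-values or label the results as unadjusted and hypothesis-generating. The cost is a little extra analysis and, if regions are selected by q-value, fewer regions flagged.
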